## Protocol Template Form

Item 1 UTHSCSA Tracking Number	HSC20150859H
--------------------------------	--------------

Item 2 Abstract / Project Summary	Provide a succinct and accurate description of the proposed research. State the purpose/aims. Describe concisely the research design and methods for achieving the stated goals. This section should be understandable to all members of the IRB, scientific and non-scientific. DO NOT EXCEED THE SPACE PROVIDED.
-----------------------------------	--

**Purpose/Objectives:** Nausea is a common symptom encountered in the Emergency Medical Services (EMS) environment that is often treated with oral or intravenous anti-emetic medications. **Research Design/Plan:** This will be a randomized equivalence study comparing the reduction in a patient's reported level of nausea after treatment with either Ondansetron or Isopropyl Alcohol

**Methods:** Patients who report nausea and/or vomiting in the normal evaluation and care of after calling 911 for Emergency Medical Care will be offered enrollment in the study. A short script will be attached to the outside of each study packet providing information about the study and its risks and benefits. Verbal or written (waiver of informed consent will be requested) permission will be obtained to start randomization. If the patient agrees to enroll then the study packet will be opened and utilized. All Advanced Life Support Ambulances in the San Antonio Fire Department will have sealed numbered opaque boxes or envelopes with either: 70% Isopropyl Alcohol swabs or ondansetron. Six Visual Nausea Severity Scoring cards will be provided with a marking pen to record timed nausea levels before and upon arrival to the Emergency Department and 15 minutes after treatment whichever comes first.

**Clinical Relevance:** This treatment has not been studied in the unique environment encountered by Paramedics in the Pre-Hospital setting. If this treatment is found to be effective, it may offer a very simple, extremely inexpensive and non-invasive (basic life support) approach for the treatment of nausea.

Item 3 Background	

Describe past experimental and/or clinical findings leading to the formulation of your study.
 
For research involving unapproved drugs, describe animal and human studies.
 
For research that involves approved drugs or devices, describe the FDA approved uses of this drug/device in relation to your protocol.
	
Nausea is a common symptom encountered in the Emergency Medical Services (EMS) environment that is often treated with oral or intravenous anti-emetic medications. Post-operative patients with modern anesthesia techniques and processes still have a 20-30% incidence of Nausea and/or vomiting. Nausea is a complicated symptom that is tough to arise from the vomiting center in the lateral reticular formation in the brainstem. Afferent inputs from the cerebellum, higher cortical centers, the vestibular apparatus, the glossopharyngeal nerve and the vagal nerve inputs contribute to the process of the perception of nausea. Chemoreceptors in the Chemoreceptor Trigger Zone (CTZ) are located on the brain surface and are highly vascularized leading to increased exposure to neurotransmitters such as Serotonin (5-HT-3), histamine (H1) acetylcholine and dopamine. Blocking such neurotransmitter stimulation with targeted medications such as antihistamines or 5-HT-3 antagonists such as Ondansetron.
 
Nausea is a common symptom encountered in the Emergency Medical Services (EMS) environment that is often treated with oral or intravenous anti-emetic medications. Many patients do not respond well to this therapy, and EMS services that have only basic life support (BLS) capabilities may not have any good treatment currently. Additionally, because of the configuration of modern day ambulances, the patient is transported in a rear facing position in the patient compartment with very limited view of the environment. This method of transport frequently causes motion sickness.
 
Motion sickness is thought to be caused by inadequate adaptation of the body to conflicts between vestibular, visual, other proprioceptive inputs and inhibition of the vestibular cerebellum. Common therapies may include antihistamines, benzodiazepines, tricyclic antidepressants and/or scopolamine. 3 Sakata

	
Behavioral strategies such as watching the true horizon, steering the vehicle, tilting head into turns and laying down with eyes closed have been shown to alleviate some symptoms of motion sickness. But these strategies are not available in the EMS environment. Scopolamine administered well before motion stimulus has been shown to prevent motion sickness and acute treatment is best when using sedating antihistamines. Non-sedating antihistamines, Ondansetron and ginger root have not been found to effectively prevent nor treat motion sickness.
 
Multiple agents have been studied for the treatment of nausea in the emergency department with equivalency of effect and time on onset. Common agents include ondansetron, metoclopramide, promethazine and prochlorperazine. Such agents have also been used in the EMS environment to some degree, but require parenteral administration with exposure to the risks for side effects or sedation. There are also no options at the BLS level. Post-operative oxygen therapy has not been shown to decrease post nausea after c-section delivery which is disappointing as this is a ubiquitous therapy in the EMS environment of care, is inexpensive and easy to administer. Ondansetron has been shown to be safe and effective in the prehospital environment with a low incidence of side effects but cost and need for parenteral administration is often a barrier to care.
 
Multiple studies have shown Isopropyl Alcohol (IPA) 70% aromatherapy to be as effective as Ondansetron with a more rapid onset of nausea relief. This therapy was performed by holding a folded saturated 70% IPA pad under the nares with the patient inhaling the vapors. The patient is simply instructed to take three deep breaths through their nose. In animal experiments, toxicity from inhalation of IPA is very low at doses allowable by inhalation as compared with dermal or oral ingestion. Dermal application of IPA is routinely used by EMS personnel to cleanse the area of skin immediately surrounding the insertion point of an intravascular catheter for medication administration, or blood draw.

Item 4 Purpose and rationale Insert purpose, objectives and research questions/hypotheses here. If you cut and paste from another document, make sure the excerpted material answers the question	Insert purpose: IPA Therapy may offer a very inexpensive, easy to administer, and effective alternative to medication therapy for nausea and vomiting in the prehospital

Item 5 Study Population(s) Being Recruited  In your recruitment plan, how many different populations of prospective subjects do you plan to target? Provide number: 1	Identify the criteria for inclusion :	Identify the criteria for exclusion :
--	--	--

e.g., a population can be individuals with type 2 diabetes controlled with diet and/or a population of healthy controls. Or a population can be individuals attending an education program, etc.
 
List each different population on a separate row and provide a short descriptive label: (e.g., normal-healthy, diabetics, parents, children, etc.)
 
To add rows use copy & paste
		

EMS patients complaining of nausea
	
Adults (non-pregnant) age 18 years or older with a symptom of nausea and/or vomiting requiring treatment by EMS
	
 
• Children not yet 18 years of Age
 
• Prisoners or those under arrest
 
• Patients known or suspected to be Pregnant
 
• Clinical Intoxication
 
• Patients unable to provide informed consent
 
• Recent Upper respiratory Tract infection
 
• Inability to follow instructions
 
• Inability to inhale through Nares
 

#### Item 6

**Research Plan / Description of the Research Methods a.** *Provide a comprehensive narrative describing the research methods. Provide the plan for data analysis (include as applicable the sample size calculation).*


Step-by-Step Methods:
 
RECRUITMENT AND RANDOMIZATION PROCESS Patients who report nausea and/or vomiting in the normal evaluation and care of after calling 911 for Emergency Medical Care will be offered enrollment in the study. A short script will be attached to the outside of each study packet providing information about the study. Verbal (waiver of documentation informed consent will be requested) permission will be obtained to start randomization. If the patient agrees to enroll then the study packet will be opened and utilized.
 
PROCEDURES AND LOGISTICS All Advanced Life Support Ambulances in the San Antonio Fire Department will have sealed numbered opaque boxes or envelopes with either:
 
 
• Three large 2 ply 70% Isopropyl Alcohol swabs
 
 
OR
 
 
• Ondansetron (Zofran) 4mg for IV/IM use (standard of care)
 
 
These study packets will have similar weight, shape and contour despite the contents. If needed, props may be included to make packages similar in weight, contour or sound when shaken so as to not reveal its true contents. The goal is to enroll at least 400 patients over a 1 year period.
 
For each arm, the package will contain a step by step instruction checklist. Six Visual Nausea Severity Scoring cards will be provided with a marking pen to record timed nausea levels before and upon arrival to the Emergency Department and 15 minutes after treatment whichever comes first. The treatment protocol for each arm will be:
 
70% Isopropyl Alcohol
 
 
1. Mark Time and Visual Nausea Severity Score 0-10
 
2. Remove alcohol prep with gloved hand
 
3. Place under nares of the patient
 
	
--	--

4. Instruct the patient to take three separate deep inhalations of the Isopropyl vapors through their nose
5. Record time of treatment on back of first Visual Nausea Severity Score card.
6. Mark time and Subsequent Visual Nausea Severity Scores upon arrival to the Emergency Department at indicated time intervals.
7. If patient still has significant nausea and or vomiting after ten minutes provide rescue Ondansetron therapy with 4mg of Ondansetron slow IV push or IM
8. Mark time and Visual Nausea Severity Score upon arrival to the Emergency Department on third card.
9. Document all interventions on electronic Patient Care record as per usual procedures.
10. Complete Paramedic evaluation tool.
11. Envelope or box, with Consent, score cards and Paramedic evaluation tool will be returned to Medic Officer on duty and a new study packet will be replaced.
12. Used Study Packets will be collected by the Investigators

Ondansetron 4mg IV/IM (standard of care)

1. Mark Time and Visual Nausea Severity Score 0-10 on first enclosed card.
2. Start IV if not already done so.
3. If unable to obtain IV access in two attempts use intramuscular route.
4. Inject 4mg of Ondansetron slow IV push or IM.
5. Record time of treatment on back of first Visual Nausea Severity Score card.
6. Mark time and Second Visual Nausea Severity Score upon arrival to the Emergency Department or 10 minutes after treatment whichever comes first.
7. If patient still has significant nausea and or vomiting after ten minutes provide rescue an additional dose of Ondansetron therapy with 4mg of Ondansetron slow IV push or IM
8. Mark time and Visual Nausea Severity Score upon arrival to the Emergency Department on third card.
9. Document all interventions on electronic Patient Care record as per usual procedures.
10. Complete Paramedic evaluation tool.
11. Envelope or box, with Consent, score cards and Paramedic evaluation tool will be returned to Medic Officer on duty and a new study packet will be replaced.
12. Used Study Packets will be collected by the Investigators.

Data Analysis Plan: A secure excel spreadsheet tool will be used to abstract data from the research data collection documents and the EMS electronic patient care record. The patient will only be identified by the randomization number, incident number, age (if greater than 89 age will be indicated by <89 years), sex and date of service in the database and on all study packet materials. All relevant time intervals and Visual Nausea Severity Scores will be recorded for enrolled patients. Time to treatment will be compared between the two arms of the study as well as changes in Visual Nausea Severity Scores. Treatment failures requiring additional Ondansetron will be characterized. Paramedic will be asked to evaluate the treatment provided for ease of use, time needed to complete the treatment and their impression of effectiveness of the assigned treatment. T-test and confidence intervals will be utilized to determine statistical significance.

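### The trial is labelled an equivalence study, but its stated purpose runs one way and the planned significance test can show neither equivalence nor non-inferiority

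*Combined protocol and SAP*

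**What the plan says.** **Design label.** The Research Design/Plan entry of Item 2 reads: "This will be a randomized equivalence study comparing the reduction in a" patient's reported nausea between the two treatments. The label is not repeated in Item 6.

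**Purpose.** Item 4: "IPA Therapy may offer a very inexpensive, easy to administer, and effective alternative to medication therapy for nausea and vomiting in the prehospital" (the visible sentence stops there). Clinical Relevance in Item 2: "If this treatment is found to be effective, it may offer a very simple, extremely inexpensive and non-invasive (basic life support) approach". Both look in one direction, and neither sets an upper limit on alcohol's benefit.

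**Expectation.** The Item 3 background says that earlier studies showed alcohol "to be as effective as Ondansetron with a more rapid onset of nausea relief".

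**Analysis.** The Data Analysis Plan in Item 6 says: "Time to treatment will be compared between the two arms of the study as well as changes in Visual Nausea Severity Scores". Its only inferential statement is: "T-test and confidence intervals will be utilized to determine statistical significance". It gives no margin, alpha, sidedness, primary endpoint, primary time point or rule for success.

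**The concern.** An equivalence claim needs the difference bounded on both sides. A cheap, non-invasive alternative is useful if it is no worse than the standard, and nothing in the visible purpose uses the upper bound. The background expects faster onset and the scores are taken early (Item 2 mentions 15 minutes or hospital arrival; step 6 of the ondansetron arm mentions 10 minutes or arrival). A lead for alcohol at the assessment is therefore plausible.

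Two things are at stake. First, the written analysis does not answer the declared question. A t-test of zero difference cannot show that two treatments are similar, or that one is no worse, and a non-significant result could be misread as equivalence. Second, if the sponsor repairs this only by adding a margin and a two-sided equivalence rule, power goes to an upper bound the purpose does not need, and a sufficiently large alcohol advantage would miss the declared aim.

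**Working it through.** **Inputs from the documents.** Enrolment goal of at least 400 in total (Item 6). Outcome scale: "Mark Time and Visual Nausea Severity Score 0-10" (Item 6, step 1). The goal of 400 has no derivation, so there is no stated calculation to reproduce.

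**Assumed inputs, none stated.** 1:1 allocation (200 per arm); SD of the change in score 3 points (range 2 to 3.5); margin m of 1, 1.5 or 2 points; two-sided 95% interval; no dropout. Let d be the true advantage of alcohol in points.

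**Formulas** (normal approximation, Φ the standard normal distribution function):
- SE = SD × √(2/200); for SD 3 this is 0.30.
- Equivalence (95% interval wholly within ±m): Φ((m − d)/SE − 1.96) − Φ((−m − d)/SE + 1.96).
- Non-inferiority (lower 95% limit above −m): Φ((m + d)/SE − 1.96).

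**Worked case, m = 1, SD 3.**
- d = 0: 1/0.30 − 1.96 = 1.373. Equivalence = Φ(1.373) − Φ(−1.373) = 83.0%. Non-inferiority = Φ(1.373) = 91.5%.
- d = 0.5: equivalence = Φ(−0.293) − Φ(−3.04) = 38.3%. Non-inferiority = Φ(3.04) = 99.9%.

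**Results for SD 3, by margin.**

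| Margin | Alcohol better by | Equivalence | Non-inferiority |
|---|---|---|---|
| 1 | 0 | 83.0% | 91.5% |
| 1 | 0.5 | 38.3% | 99.9% |
| 1 | 1.0 | 2.5% | >99.9% |
| 1.5 | 0.5 | 91.5% | >99.9% |
| 1.5 | 1.0 | 38.5% | >99.9% |
| 2 | 0.5 | 99.9% | >99.9% |
| 2 | 1.0 | 91.5% | >99.9% |

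The 2.5% arises because d equals the margin there. It is the one-sided error rate by construction and would be the same for any SD in the range.

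**Effect of the SD at margin 1.**

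| SD | Equal arms: equivalence / non-inferiority | Alcohol 0.5 better: equivalence / non-inferiority |
|---|---|---|
| 2 | 99.8% / 99.9% | 70.5% / >99.9% |
| 2.5 | 95.9% / 97.9% | 51.6% / >99.9% |
| 3 | 83.0% / 91.5% | 38.3% / 99.9% |
| 3.5 | 63.0% / 81.5% | 28.8% / 99.0% |

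With a 90% interval (one-sided 0.05) instead, margin 1 and SD 3 give 90.9% against 95.4% for equal arms, and 50.8% against >99.9% at 0.5 better.

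**The test as written.** With SD 3, a two-sided 5% t-test has 80% power for (1.96 + 0.84) × 0.30 = 0.84 point.
- Alcohol truly 1 point better: significant in its favour with probability Φ(1/0.30 − 1.96) = 91.5%.
- Alcohol truly 0.5 point worse: significant against it only Φ(0.5/0.30 − 1.96) = 38.5% of the time, so non-significant about 61% of the time. Non-significance is therefore no evidence that alcohol is as good.

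**Patients per arm for 80% power, equal arms, margin 1, SD 3.** Non-inferiority: 2 × (3 × (1.96 + 0.8416)/1)² = 141.3, so 142. Equivalence: 2 × (3 × (1.96 + 1.2816)/1)² = 189.1, so 190.

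**The case against.** A reader might infer that the plan treats any better result for alcohol as a failure. The documents do not support that. They do not describe the equivalence as two-sided, and no rule defines success or failure. The written t-test would usually report a 1-point advantage as significant in alcohol's favour. Even under strict equivalence, an advantage whose interval stays inside the margin would pass.

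Further points on the other side:
- The label appears once, in an abstract meant for lay as well as scientific board members. The background uses the idea of equivalency loosely, so the sponsor may not have intended a two-bound test.
- The loss depends on a margin nobody has set. At margin 2 and SD 3 it is small.
- An expectation of equal effect with faster onset is close to an equivalence hypothesis. No size is given for any early lead.
- The visible Item 4 sentence is incomplete, so a further objective may have been lost in conversion.
- Equivalence is a legitimate design choice, and the missing margin is the more basic gap.

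These points limit the size of the concern and rule out the strong reading. The mismatch remains: the label, the one-directional purpose and the difference test do not fit together. Adding a margin while keeping equivalence would leave the upper bound in place.

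**Conclusion.** The concern holds as a mismatch between label, purpose and analysis. It is not a finding that the plan penalises a good result. As written, the analysis can establish neither equivalence nor non-inferiority. If a conventional two-sided equivalence rule were adopted, only an alcohol advantage large enough to push the interval past the upper margin would miss the aim.

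How much that costs depends on assumptions the documents do not settle. It is substantial at a margin of 1 point with SD 3 and minor at a margin of 2. The conclusion also rests on the visible part of Item 4. The change is worth making because it costs little and answers the question that the purpose poses.

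**What to change.** 1. In Item 2, describe the trial as a randomized non-inferiority study.
2. In the Item 6 Data Analysis Plan, replace the significance-test sentence with this rule: alcohol is non-inferior if the lower limit of the two-sided 95% confidence interval for (reduction on alcohol minus reduction on ondansetron) lies above minus a prespecified, justified margin, at one named primary time point.
3. Add: if non-inferiority is shown, superiority is concluded if the same limit is above 0. This spends no further alpha, because superiority is examined only after non-inferiority and on the same interval.
4. Then derive the sample size from the chosen margin, SD, alpha and power.

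**Cost.** Text changes in Items 2 and 6, with no extra patients or data. The sponsor must choose and justify a margin and settle one primary time point; the score timings in Items 2 and 6 need to be reconciled for this. The trial gives up the claim that alcohol's benefit over ondansetron is bounded above, which the visible purpose does not use.

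### Eligibility admits patients who vomit without nausea, although the score outcome is change in nausea; any patients with a baseline of 0 dilute a true difference, by an amount the documents cannot fix

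*Combined protocol and SAP*

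**What the plan says.** Item 2 defines the design: "This will be a randomized equivalence study comparing the reduction in a patient's reported level of nausea after treatment". In Item 5 the row label is "EMS patients complaining of nausea", but the inclusion criterion in the same row is "Adults (non-pregnant) age 18 years or older with a symptom of nausea and/or vomiting requiring treatment by EMS". The recruitment text in Item 6 is equally wide: "Patients who report nausea and/or vomiting in the normal evaluation and care of after calling 911 for Emergency Medical Care". No section sets a minimum nausea score, and none of the eight exclusions removes low scorers.

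On the order of events, Item 6 says: "If the patient agrees to enroll then the study packet will be opened and utilized". The checklist is inside the packet, and its first step is "Mark Time and Visual Nausea Severity Score 0-10". The ondansetron checklist places that first score on a card enclosed in the packet.

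The Data Analysis Plan in Item 6 compares time to treatment and changes in the nausea score between arms, and describes treatment failures that need more ondansetron. The method is one sentence: "T-test and confidence intervals will be utilized to determine statistical significance". It gives no equivalence margin, no baseline adjustment and no rule for patients with a low first score.

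**The concern.** The criterion is wider than both the label and the outcome. A patient who has vomited but is not nauseated when scored meets the criterion as written and starts at the floor of the scale, where the score can only stay or rise. A patient at 1 or 2 can gain at most 1 or 2 points. The need for EMS treatment limits trivial cases but is not a score threshold, and vomiting can satisfy it.

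In a superiority trial, patients who cannot respond cost power. In an equivalence trial the same dilution works in favour of the claim. It makes an interval more likely to fall inside whatever margin is later chosen, and a t-test more likely to be non-significant and be misread as equivalence.

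A score of 0 would come to light only once the assigned treatment is known. Dropping the patient then would be an exclusion after allocation is revealed.

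**Working it through.** The plan gives an enrolment goal of at least 400 but no SD, margin, power or baseline distribution, so there is no calculation to reproduce. Both illustrations below rest on assumed inputs.

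**1. Shrinkage of the observed difference.** Assumed: latent reductions of 4 and 2 points, SD 2, scores held to 0-10, main group with baselines uniform on 3-10, low group uniform on 0-2. By simulation the observable difference is 1.70 in the main group and 0.37 in the low group. With a share f in the low group:

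observed difference = (1 - f) x 1.70 + f x 0.37; relative loss = f x (1 - 0.37/1.70) = 0.782 f

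| f | observed difference | loss |
|---|---|---|
| 2% | 1.67 | 1.6% |
| 5% | 1.63 | 3.9% |
| 10% | 1.57 | 7.8% |
| 20% | 1.43 | 15.6% |
| 30% | 1.30 | 23.5% |

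**2. Effect on an equivalence claim.** Assumed: 200 per arm (1:1 split of 400), SD of change 2.5, mean change 3, two one-sided tests at 0.05, and a true difference among nauseated patients equal to the margin M. A share f has baseline 0 and no change in either arm. Then

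difference d = (1 - f)M; variance s² = (1 - f) x 2.5² + f(1 - f) x 3²; SE = s x √(2/200)

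P(declare equivalence) ≈ Φ((M - d)/SE - 1.645), less a lower-limit term that matters only for M = 0.5.

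For M = 1 and f = 10%: d = 0.90; s² = 5.625 + 0.81 = 6.435; s = 2.54; SE = 0.254; Φ(0.394 - 1.645) = Φ(-1.251) = 10.6%.

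| M | f = 0 | f = 10% | f = 20% |
|---|---|---|---|
| 0.5 | 4.1% | 5.6% | 7.7% |
| 1.0 | 5.0% | 10.6% | 19.6% |
| 1.5 | 5.0% | 14.6% | 32.2% |

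If a two-sided t-test at 0.05 is used instead, power to detect the 1-point difference falls from 97.9% to 94.4% and 88.3%. The chance of a non-significant result rises from 2.1% to 5.6% and 11.7%.

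**3. How much a minimum score recovers.** Assumed: bell-shaped baselines (mean 6, SD 2.5, rounded and held to 0-10), drops of 4 and 3 points with SD 2.5, floor at 0. The latent difference of 1.0 is observed as 0.75 with no minimum, 0.76 with a minimum of 1, 0.79 with a minimum of 3 and 0.83 with a minimum of 4. Only Φ((0.5 - 6)/2.5) = Φ(-2.2) = 1.4% of patients score 0 in this model, so a non-zero rule has little to remove. Much of the floor effect comes from patients with higher baselines.

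**The case against.** The strongest reply is that nothing shows such patients would be enrolled in number. The label names nausea, the background is about nausea, and patients must need EMS treatment. At shares of 2-5% the loss is only about 2-4%. This stands: the size is an assumption, and it may be small.

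Second, wide enrolment may be deliberate. Item 4 states the purpose as covering vomiting as well as nausea, and vomiting is part of the trigger for additional ondansetron, which is to be described. If the target is everyone EMS treats for either symptom, a smaller mean difference is that population's effect and not a bias. This stands in part. However, the plan has no vomiting outcome beyond that trigger, and a nausea score cannot measure benefit in someone who is not nauseated.

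Third, the missing margin is the larger gap. That is right: the second table shows how strongly the result depends on it. Dilution still works in the same direction at every margin shown.

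A reader might infer that the trial is bound to reach false equivalence, or that a minimum score of 3 is needed. The documents support neither. They give no baseline distribution and no margin, and no text justifies 3 or any other cut-off.

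**Conclusion.** The mismatch is real and can be read directly from the text: criterion and recruitment wording admit vomiting alone, the label and the score outcome concern nausea, and no step before packet opening screens out a score of 0. The direction is also clear: if the treatments differ in nauseated patients, those at the floor shrink the difference.

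The size cannot be determined. Under the assumed uniform-baseline model the loss runs from about 2% to 23-24% as the share scoring 0-2 goes from 2% to 30%. With 10% of patients at 0, the chance of wrongly declaring equivalence ranges from 5.6% to 14.6% across assumed margins of 0.5 to 1.5 points. This is a cheap correction worth making; it is not evidence that the trial's result would be wrong.

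**What to change.** Reconcile the Item 5 criterion and the Item 6 recruitment text with the label. Require current nausea, with or without vomiting, confirmed by a non-zero 0-10 score. Ask for that score with the script on the outside of the packet and record it before the packet is opened.

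Whether to set a higher minimum is for the investigators to choose and justify; 3 is only an example. It would lessen the floor effect without removing it. A pre-specified analysis by baseline score is an alternative that leaves eligibility unchanged, but it too needs the score taken before opening. Baseline adjustment and a stated margin would help interpretation under either option.

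Cost: one extra question before opening, since the existing first score is taken inside the packet; vomiting-only patients not enrolled; slightly slower recruitment toward 400; and a conclusion limited to patients with nausea, which is narrower than the purpose in Item 4. That purpose should be reworded to match.

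### Six score cards are supplied, but the two checklists set different and partly undefined scoring times, with no shared fixed time before ten minutes

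*Combined protocol and SAP*

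**What the plan says.** The scoring schedule appears in three places, all in Item 6; the Abstract (Item 2) repeats the first.

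- **Narrative (Procedures and Logistics).** "Six Visual Nausea Severity Scoring cards will be provided with a marking pen to record timed nausea levels", before treatment and then "upon arrival to the Emergency Department and 15 minutes after treatment whichever comes first".
- **Ondansetron checklist.** Step 1: "Mark Time and Visual Nausea Severity Score 0-10 on first enclosed card". Step 6: "Mark time and Second Visual Nausea Severity Score upon arrival to the Emergency Department or 10 minutes after treatment whichever comes first". Step 8: "Mark time and Visual Nausea Severity Score upon arrival to the Emergency Department on third card".
- **Alcohol checklist.** Step 1: "Mark Time and Visual Nausea Severity Score 0-10". Step 6: "Mark time and Subsequent Visual Nausea Severity Scores upon arrival to the Emergency Department at indicated time intervals". Step 8 has the same wording as ondansetron step 8, again on card three.

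In both checklists step 5 records the time of treatment on the back of the first card, and step 7 allows rescue ondansetron once ten minutes have passed.

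The Background (Item 3) reports earlier studies in which alcohol matched ondansetron "with a more rapid onset of nausea relief". The Data Analysis Plan compares time to treatment and change in score between the arms. It names no analysis time for the change and no comparison of early relief.

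**The concern.** A crew working from the checklist will follow its numbered steps, so those steps decide what is measured. Followed as written, they score the two arms on different schedules, one of which is undefined. Two things are at stake.

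1. **Early relief.** The background singles out speed of relief as a feature of alcohol. Time to treatment does not measure it: that is when the swab or drug was given, not when nausea eased. Comparing early relief needs scores at the same short times after treatment in both arms.
2. **A score before rescue.** Rescue in either arm is ondansetron. A score taken after rescue reflects the rescue dose as well as the assigned treatment. A change in score that describes the assigned treatment alone needs a score before that point, taken at a comparable time in each arm.

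Scores not taken during transport cannot be recovered later.

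**Working it through.** No formula applies and the plan states no figure to reproduce, so the check is a count of cards and a comparison of times.

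**Cards, against six supplied**

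| | Ondansetron | Alcohol |
|---|---|---|
| Baseline | 1 (step 1) | 1 (step 1) |
| Intermediate | 1 (step 6) | number not stated (step 6, plural) |
| ED arrival | 1 (step 8, card three) | 1 (step 8, card three) |
| Total named | 3 | 3 if the card-three label governs; up to 6 if the plural does |
| No stated use | 6 − 3 = 3 | 6 − 6 = 0 to 6 − 3 = 3 |

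**Times.** Let T be the minutes from treatment to ED arrival. The documents give no distribution for T, so the cases are set out by range.

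| | Narrative | Ondansetron | Alcohol |
|---|---|---|---|
| T up to 10 | T | T (steps 6 and 8 coincide) | T, plus unstated times |
| T from 10 to 15 | T | 10 and T | T, plus unstated times |
| T over 15 | 15 | 10 and T | T, plus unstated times |

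The narrative column takes its closing phrase to mean the earlier of the two events, although the two are joined by *and*.

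Four things follow.

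- With T up to 10, ondansetron yields only two distinct scores, baseline and arrival. Both arms then have an arrival score no later than ten minutes, but at an elapsed time set by the journey.
- With T over 10, ondansetron has a score at 10 minutes, placed before the rescue step. Alcohol's only clearly timed post-treatment score is ED arrival, which can follow rescue.
- With T over 15, the narrative, the ondansetron checklist and the alcohol checklist give three different answers for the first clearly timed score after treatment: 15, 10 and T.
- In no row is there a fixed time before 10 minutes, common to both arms, that does not depend on the journey.

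**The case against.** **Onset is not an objective.** The stated comparison is equivalence in reduction of nausea, and Item 4 gives cost, ease and effectiveness as the purpose. Faster onset is one background sentence about earlier studies. This stands: leaving onset untested contradicts no stated aim, and the early comparison belongs among secondary analyses. It does not answer the mismatch in schedules, which also affects the score change that the plan does intend to compare.

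**The alcohol checklist may use more than three cards.** Its step 6 is plural and could cover all six. This also stands. A reader might infer that both arms use only three cards, but that is certain only for ondansetron. For alcohol the defect is that the intervals are not stated.

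**Early scores may exist.** A reader might infer that nothing is scored before ten minutes and that any onset difference is invisible. The document does not support that. The ondansetron second score moves earlier when the ED is reached sooner, the unstated alcohol intervals could include early times, and treatment and scores are all timed. What remains is that such scores would depend on journey length or on a crew's guess, and need not be comparable between arms.

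**More scores, more precision.** A reader might infer a gain in precision from averaging extra scores. The plan gives no correlation between scores and proposes no averaging, and averaging early with late scores would change the quantity estimated. No such gain is claimed here.

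**Conclusion.** The point holds as an inconsistency in what is measured, with a cheap remedy. Certain from the text: six cards against three named scores under ondansetron; an alcohol step that relies on intervals given nowhere; 15 minutes in the narrative against 10 in the ondansetron checklist; and no fixed time before 10 minutes common to both arms. It follows that early relief cannot be reliably compared and that no comparable score before the ten-minute rescue point is assured in both arms.

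The size is three of six cards without a stated use under ondansetron and none to three under alcohol. The effect on the estimated difference cannot be quantified, because the document gives neither transport times nor the frequency of rescue. How often the alcohol arrival score would follow rescue depends on both.

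The conclusion assumes that crews follow the checklists as written and that the alcohol intervals are not set out in packet material outside this document. It does not show that the equivalence comparison fails.

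**What to change.** 1. Reconcile the card count and scoring times across the Abstract, the Item 6 narrative and both checklists, including 15 against 10 minutes.
2. In alcohol step 6, replace the reference to unspecified intervals with stated times.
3. Give spare cards the same fixed early post-treatment times in both checklists, for example 2 and 5 minutes, and keep the later scores. With the three scores already named, this uses 3 + 2 = 5 of the six cards. Renumber them, since ED arrival would no longer fall on card three.
4. In the Data Analysis Plan, add a secondary between-arm comparison of change from baseline at those early times, with confidence intervals and the number of missing early scores in each arm. Time these scores from treatment, which both checklists already record. Packet opening is not recorded in either checklist, so an outcome timed from it would need a new entry.

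The cost is a few seconds of crew time for two extra marks, some missed early cards, and one added secondary analysis. No dose or rescue rule changes.
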